8.5.3 Analysis of the exploratory variable(s)

The MAGE will be calculated for each patient by taking the arithmetic mean of blood glucose increases or decreases (from blood glucose nadirs to peaks or vice versa) when both ascending and descending segments exceed the value of 1 SD of the blood glucose concentration in a 24 hour period. The proportion of time that patients had plasma glucose measurements <70 mg/dL, ≥ 70 mg/dL and ≤ 180 mg/dL, and >180 mg/dL will be calculated as the time period the glucose level falls into the pre-specified criteria, divided by the total time period. Detailed calculation will be described in the SAP.

Tertiary endpoints will be analyzed using a similar MMRM model to the primary and secondary endpoints, with the baseline value of the dependent variable included as a fixed effect factor.

Daily 24-hour glucose profile collected during the 1 week lead-in period and during Week 10 will be summarized descriptively and plotted. The difference and/or similarity will be discussed.

8.5.4 Interim analysis

An interim analysis with the objective of determining enrollment targets for the remainder of the study may be performed at the Study Director's discretion at approximately the time when the 30th patient from each study arm completes the 10-week visit with the primary efficacy evaluation. The actual timing of the interim analysis will be determined by the Study Director

and will depend on the observed enrollment rates and the distribution of enrollment over the study sites. An unblinded statistician independent of the study conduct will perform the interim analysis and communicate the results to a Study Director designated committee that will make necessary decisions and communicate those to the study team for implementation.

The focus of this interim analysis will be the population mean treatment difference, treatment minus placebo, in the change from baseline for the 24-hour mean glucose as measured by the patient CGM devices, at the Week 10 visit (using the definition of the primary endpoint as defined in Section 8.4.1). The data used for this analysis will come from the patient's 24 hour mean evaluations at both the 4-week and the 10-week visits, and patients having only a 4-week visit will be included in this analysis. The model used for the evaluation of the population mean 10-week treatment difference will assess the relationship of the Week 4 and Week 10 results in order to achieve greater precision for the Week 10 decision.

A Bayesian methodology will be used to project the eventual success at the planned final analysis (statistical significance at $p = 0.05$ two-tailed) as described in Section 8.4.1 of the study protocol. The model will utilize a bivariate normal-Wishart conjugate prior assuming very little information regarding the population treatment differences and population error covariance matrix, and will eventually lead to a posterior distribution of the population Week 10 mean treatment difference conditioned on the interim observed mean differences at Weeks 4 and 10, and the observed error covariance matrix (Week 4 variance, Week 10 variance, Week (4, 10) covariance). From this posterior distribution, the predicted power of the final primary efficacy comparison at the planned final sample size will be calculated by computing the conditional power at a fixed population mean Week 10 difference given the results of the interim analysis, then averaging over all population mean differences using the posterior distribution obtained from the interim analysis. This is the interim average power of final success at the original planned sample size given the interim results, and decisions will be based on this interim average power.

The decision criterion will have the following form:

- a. Curtail enrollment (stop enrollment), continue all currently enrolled patients to their final visit and perform the final analysis on the reduced set of patients (at $p = 0.05$ two-tailed). This decision will occur under either of the 2 following interim analysis results, but only the higher level decision to stop further enrollment not which of the underlying conditions that has been met will be communicated to the Study Director designated committee and the study team.
 - (Early futility) if the interim average power is less than 20%, or
 - (Early efficacy) the interim average power is greater than 90%.

- b. Continue Enrollment. If the interim average power is greater than or equal to the early futility boundary of 20%, and less than or equal to the early efficacy boundary of 90%, then at the Study Director designated committee's discretion the study will either:
- Continue to its planned final sample size and perform the final 10-week treatment comparison as originally planned (at $p = 0.05$, two-tailed), or
 - Continue with a potentially updated enrollment target. The unblinded statistician will provide the interim sample sizes and an updated average power for the trial given the interim results to guide decision making about an updated enrollment target for the study. In this case, any other decision outside the scope of the criteria above an appropriate adjustment will be determined by the unblinded statistician to preserve the overall p-value inherent with this decision using a Lan-Demets methodology.

Further details of the methodology will be described in the SAP.

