3.7 Methods for unblinding

Individual treatment codes, indicating the treatment randomization for each randomized patient, will be available to the Investigator(s) from the IVRS/IWRS. Routines for this will be described in the IVRS/IWRS user manual that will be provided to each center.

The treatment code should not be broken except in medical emergencies when the appropriate management of the patient requires knowledge of the treatment randomization. The Investigator documents and reports the action to AstraZeneca, without revealing the treatment given to patient to the AstraZeneca staff.

AstraZeneca retains the right to break the code for serious adverse events (SAEs) that are unexpected and are suspected to be causally related to an investigational product and that potentially require expedited reporting to regulatory authorities. Treatment codes will not be broken for the planned analyses of data until all decisions on the evaluability of the data from each individual patient have been made and documented.

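### Section 8.5.4 gives two incompatible rules on what the interim committee may learn, and in the continue branch supplies an average power that approximately reveals the interim effect

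*Protocol*

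**What the plan says.** All of the following is in Protocol section 8.5.4 unless another section is named.

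- **General rule.** The unblinded statistician, who must be independent of study conduct, will "communicate the results to a Study Director designated committee that will make necessary decisions" and pass those decisions to the study team. No limit is set on the results.
- **Stop branch** (interim average power below 20% or above 90%). "only the higher level decision to stop further enrollment not which of the underlying conditions that has been met will be communicated" to the committee and the study team.
- **Continue branch** (average power from 20% to 90%). Here "then at the Study Director designated committee's discretion the study will either" keep the planned size or move to an updated target. For the second option, "The unblinded statistician will provide the interim sample sizes and an updated average power for the trial given the interim results", to guide that decision. The sentence names no recipient, but the decision it serves is the committee's.
- **Timing.** The look may take place at "approximately the time when the 30th patient from each study arm completes the 10-week visit with the primary efficacy evaluation".
- **Blinding elsewhere.** Section 3.7 says: "Treatment codes will not be broken for the planned analyses of data until all decisions on the evaluability of the data" have been made and documented. Section 8.1 keeps everyone involved in the analysis blinded until database lock. Section 3.6 gives an external statistician and a sponsor medical lead access to unblinded data. Neither 3.7 nor 8.1 mentions the interim analysis.

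**The concern.** The stop-branch rule has a clear purpose: people who can influence the rest of the trial should not know which way the data point. A committee that has been given the results knows whether average power was below 20% or above 90%, so the general rule defeats the stop-branch rule.

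The continue branch has a second, separate weakness. Enrollment, retention and evaluability decisions are all still open there. The body choosing the new target is to be guided by a number computed from the unblinded effect, and the protocol does not require that body to be outside study conduct. If average power can be turned back into the effect, the committee is in practice unblinded. The Lan-DeMets adjustment that the section mentions protects the type I error. It does not address conduct that changes because someone knows the effect.

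**Working it through.** **1. The two communication rules side by side.** The general rule sends the results to the committee. The stop-branch rule sends the same committee the decision alone. The results include the average power, or allow it to be computed, and the thresholds are printed in the protocol. A statistician who follows the first rule breaks the second. No arithmetic is needed.

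**2. The plan's own figure.** Section 8.2 gives 39 per arm, a difference of 18 mg/dL, SD 24 mg/dL (stated for Week 4) and two-sided 0.05, for 90% power. The standard error is 24 × √(2/39) = 5.43 and 18/5.43 = 3.31, so the normal approximation gives Φ(3.31 − 1.96) = 91.2%. The noncentral t gives 90.5%. The stated 90% is reproduced.

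**3. Can average power be turned back into the effect?** The section defines average power as conditional power averaged over the posterior of the Week 10 difference, with a prior carrying very little information.

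Assumptions: flat prior, known variance, Week 10 data only, 30 per arm at the look, and a final size N of 39 per arm (the section 8.2 completers) or 55 (all randomized). Let t = 30/N and let z be the interim test statistic. Then

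- average power = Φ((z/√t − 1.96) / √((1−t)/t))
- inverted: z = √t × (1.96 + Φ⁻¹(average power) × √((1−t)/t))
- standardized effect = z × √(2/30) = z × 0.258

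Worked case, average power 50%, where Φ⁻¹ = 0:

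- N = 39: t = 0.769, √t = 0.877, z = 0.877 × 1.96 = 1.719, effect = 0.444 SD
- N = 55: t = 0.545, √t = 0.739, z = 0.739 × 1.96 = 1.448, effect = 0.374 SD

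| Average power | N = 39: effect in SD units | N = 39: mg/dL at SD 20 / 24 / 30 | N = 55: effect in SD units | N = 55: mg/dL at SD 20 / 24 / 30 |
|---|---|---|---|---|
| 20% | 0.339 | 6.8 / 8.1 / 10.2 | 0.227 | 4.5 / 5.5 / 6.8 |
| 50% | 0.444 | 8.9 / 10.7 / 13.3 | 0.374 | 7.5 / 9.0 / 11.2 |
| 80% | 0.548 | 11.0 / 13.2 / 16.4 | 0.520 | 10.4 / 12.5 / 15.6 |
| 90% | 0.603 | 12.1 / 14.5 / 18.1 | 0.597 | 11.9 / 14.3 / 17.9 |

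A simulation at N = 39 returned 0.500 and 0.801 for targets of 0.50 and 0.80, so the inversion is correct under its assumptions.

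**4. What the number adds.** The bare message to continue already brackets the standardized effect, at 0.34 to 0.60 SD (N = 39) or 0.23 to 0.60 SD (N = 55), because the thresholds are public. The average power, with the sample sizes and the N it refers to, narrows that bracket to nearly a point on the standardized scale.

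**5. Where the inversion is only approximate.** The planned model is bivariate. It uses Week 4 and Week 10 together, includes patients with Week 4 data only, and estimates the covariance matrix under a Wishart prior. The average power therefore depends on more than the Week 10 estimate. A value in mg/dL also needs an SD. The protocol prints 24 mg/dL for Week 4, gives no separate Week 10 value, and does not say that an SD is supplied. The range of 20 to 30 is an assumption.

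**The case against.** **The disclosure and the concealment rule are in different branches.** A reader might infer that supplying average power directly contradicts hiding the stopping condition. It does not. Average power is supplied only when enrollment continues, and then no stopping condition has been met, so there is none to hide. This objection stands. The literal contradiction is between the general rule and the stop-branch rule; the continue-branch disclosure is a separate weakness.

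**The general sentence is introductory and the later one specifies it.** That is a fair reading of intent. But the text neither limits the results nor says that the later rule overrides, so two statisticians could act differently and each cite the section.

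**Average power is not a one-to-one function of the Week 10 estimate.** Correct under the bivariate model. A reader might infer from the inversion that the estimate in mg/dL is exactly disclosed. The documents do not support that. What remains is a close approximation on the standardized scale.

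**Bias is not shown.** Also correct. The efficacy analyses use the Modified ITT set, so compliance judgments affect only the supportive Evaluable set. CGM readings are hidden from the patient during recording (section 5.2.6.2), patients and investigators stay blinded (section 3.6), and nothing sends average power to sites. The claim must be one of risk.

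**Membership and confidentiality may be set in the SAP or a charter.** Section 8.5.4 leaves further methodology to the SAP, and silence on membership alone would be no finding. Who receives what, however, is stated in the protocol, and stated inconsistently.

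**Lesser points.** A per-arm trigger might suggest that whoever sets the timing must be unblinded. The count is approximate, and under 1:1 blocked allocation about 60 pooled completers serves as well. Section 3.7 might seem to be breached by any interim look. It can be met by settling evaluability blind beforehand. Both are minor.

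**Conclusion.** The point holds in two parts. First, section 8.5.4 contradicts itself: the committee cannot both receive the results and be kept from knowing why enrollment stopped. This rests on the text alone. Second, in the continue branch a committee not required to be independent of study conduct is to be guided by an average power from which the standardized interim effect can be closely approximated. At 50% this is about 0.44 SD with a final 39 per arm or 0.37 SD with 55, equivalent to about 8.9 to 13.3 or 7.5 to 11.2 mg/dL if the SD lies between 20 and 30 mg/dL. The second part rests on a flat prior, known variance, Week 10 data only and 30 per arm. The Week 4 data and the actual prior would shift the figures. The consequence is an avoidable risk of operational bias; the documents do not show that bias would occur.

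**What to change.** - **General rule.** Replace the instruction to pass on the results with one to communicate only the action: stop enrollment, continue to the planned size, or continue to a stated total.
- **Continue branch.** Have the unblinded statistician derive any new total from a rule filed before unblinding and withheld from the study team, and do not supply the average power to the committee. Anyone holding the rule could still read a band of average power from the announced total, so the leak is coarsened rather than removed. That is why the rule must be withheld.
- **Alternative.** If the committee must see average power in the continue branch, state that its members are unblinded and take no part in study conduct. Keep the concealment rule for the stop branch.
- **Sections 3.7 and 8.1.** State that for the interim they are met by documenting evaluability decisions blind before the codes are released to the independent statistician.

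The cost is protocol wording and a short interim charter. Under the main option the committee loses discretion over the exact target. No additional patients or assessments are needed.

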8.5.5 Safety analysis

The number and percent of patients with an adverse event will be summarized for each treatment group. Changes from baseline to each scheduled visit for each clinical laboratory test, blood pressure and heart rate will be summarized by treatment group. In addition, the number and percent of patients with a predefined marked abnormality, using standard definitions, in clinical laboratory tests will be summarized by treatment group. Electrocardiogram data will be summarized.

8.5.6 Biomarker analysis

No biomarker analysis is planned at this time.

8.5.7 Demographic and baseline characteristics

Demographic and baseline characteristics will be summarized by treatment group as well as for all patients combined. Baseline is defined as the last measurement prior to the first randomized dose of double-blind medication. No statistical test will be carried out for comparison of any baseline measurement between the treatment groups.

9. STUDY AND DATA MANAGEMENT

9.1 Training of study site personnel

Before the first patient is entered into the study, an AstraZeneca representative will review and discuss the requirements of the Clinical Study Protocol and related documents with the investigational staff and also train them in any study specific procedures and EDC system(s) utilized.

The Principal Investigator will ensure that appropriate training relevant to the study is given to all of these staff, and that any new information relevant to the performance of this study is forwarded to the staff involved.

The Principal Investigator will maintain a record of all individuals involved in the study (medical, nursing and other staff).

9.2 Monitoring of the study

During the study, an AstraZeneca representative will have regular contacts with the study site, including visits to:

- Provide information and support to the Investigator(s)
- Confirm that facilities remain acceptable
- Confirm that the investigational team is adhering to the protocol, that data are being accurately and timely recorded in the eCRFs, that biological samples are handled in accordance with the Laboratory Manual, and that study drug accountability checks are being performed
- Perform source data verification (a comparison of the data in the eCRFs with the patient's medical records at the hospital or practice, and other records relevant to the study) including verification of informed consent of participating patients. This will require direct access to all original records for each patient (e.g., clinic charts)
- Ensure withdrawal of informed consent to the use of the patient's biological samples is reported and biological samples are identified and disposed of/destroyed accordingly, and the action is documented, and reported to the patient
- The AstraZeneca representative will be available between visits if the Investigator(s) or other staff at the center need information and advice about the study conduct.

9.2.1 Source data

Refer to the CSA for location of source data.

9.2.2 Study agreements

The Principal Investigator at the center(s) should comply with all the terms, conditions, and obligations of the CSA, or equivalent, for this study or any resulting publications. In the event of any inconsistency between this Clinical Study Protocol and the CSA, the terms of the Clinical Study Protocol shall prevail with respect to the conduct of the study and the treatment of patients and in all other respects, not relating to study conduct or treatment of patients, the terms of the CSA shall prevail.

Agreements between AstraZeneca and the Principal Investigator should be in place before any study-related procedures can take place, or patients are enrolled.

9.2.3 Archiving of study documents

The Investigator follows the principles outlined in the CSA.

9.3 Study timetable and end of study

The end of the study is defined as ‘the last visit of the last patient undergoing the study’.

The study is expected to start in the 4th quarter 2014 and to end by 4th quarter 2015.

The study may be terminated at individual centers if the study procedures are not being performed according to Good Clinical Practice (GCP), or if recruitment is slow. AstraZeneca may also terminate the entire study prematurely if concerns for safety arise within this study or in any other study with BYDUREON.

9.4 Data management by Medpace

Data management will be performed by Medpace, according to the Data Management Plan. The data collected through third party sources will be obtained and reconciled against study data.

Adverse events and medical/surgical history will be classified according to the terminology of the latest version the Medical Dictionary for Regulatory Activities (MedDRA). Medications will be classified according to the AstraZeneca Drug Dictionary. All coding will be performed by Medpace.

Data queries will be raised for inconsistent, impossible, or missing data. All entries to the study database will be available in an audit trail.

The data will be validated as defined in the Data Management Plan. Quality control procedures will be applied to each stage of data handling to ensure that all data are reliable and have been processed correctly. The Data Management Plan will also clarify the roles and responsibilities of the various functions and personnel involved in the data management process.

When all data have been coded, validated, signed, and locked, clean file will be declared. Any treatment revealing data may thereafter be added and the final database will be locked.

10. ETHICAL AND REGULATORY REQUIREMENTS

10.1 Ethical conduct of the study

The study will be performed in accordance with ethical principles that have their origin in the Declaration of Helsinki and are consistent with International Conference on Harmonisation

(ICH)/GCP, applicable regulatory requirements and the AstraZeneca policy on Bioethics and Human Biological Samples.

10.2 Patient data protection

The Informed Consent Form will incorporate (or, in some cases, be accompanied by a separate document incorporating) wording that complies with relevant data protection and privacy legislation.

10.3 Ethics and regulatory review

An institutional review board (IRB) should approve the final study protocol, including the final version of the Informed Consent Form and any other written information and/or materials to be provided to the patients. The Investigator will ensure the distribution of these documents to the applicable IRB, and to the study site staff.

The opinion of the IRB should be given in writing. The Investigator should submit the written approval to AstraZeneca before enrollment of any patient into the study.

The IRB should approve all advertising used to recruit patients for the study.

AstraZeneca should approve any modifications to the Informed Consent Form that are needed to meet local requirements.

If required by local regulations, the protocol should be re-approved by the IRB annually.

Before enrollment of any patient into the study, the final study protocol, including the final version of the Informed Consent Form, is approved by the national regulatory authority or a notification to the national regulatory authority is done, according to local regulations.

AstraZeneca will handle the distribution of any of these documents to the national regulatory authorities.

AstraZeneca will provide Regulatory Authorities, the IRB, and Principal Investigators with safety updates/reports according to local requirements.

Each Principal Investigator is responsible for providing the Ethics Committees/IRB with reports of any serious and unexpected adverse drug reactions from any other study conducted with the investigational product. AstraZeneca will provide this information to the Principal Investigator so that he/she can meet these reporting requirements.

10.4 Informed consent

The Principal Investigator(s) at each center will:

- Ensure each patient is given full and adequate oral and written information about the nature, purpose, possible risk, and benefit of the study

- Ensure each patient is notified that they are free to discontinue from the study at any time
- Ensure that each patient is given the opportunity to ask questions and allowed time to consider the information provided
- Ensure each patient provides signed and dated informed consent before conducting any procedure specifically for the study
- Ensure the original, signed Informed Consent Form(s) is/are stored in the Investigator's Study File
- Ensure a copy of the signed Informed Consent Form is given to the patient
- Ensure that any incentives for patients who participate in the study as well as any provisions for patients harmed as a consequence of study participation are described in the Informed Consent Form that is approved by an IRB

